6.6.10 Multiplicity Adjustments

With two interim efficacy analyses each testing for benefit of serum urate elevation at a onesided p < 0.001, the final primary analysis tested using a two-sided p < 0.046 ensures that the overall type I error rate is under 5%. Results from analysis of secondary efficacy endpoints and subgroup analyses will report nominal, comparison-wise p-values, recognizing that the totality of results will be evaluated in judging the potential efficacy of serum urate elevation.

6.6.11 Missing Data

Baseline values for efficacy endpoints will be determined from the last non-missing data collected prior to the first dose of study medication. The planned mixed model yields estimates that are unbiased conditional on the observed scores under a missing at random assumption. In addition, a secondary analysis of the primary endpoint will use placebo-based multiple imputation of missing data. Additional sensitivity analyses may be pursued to impute missing values or otherwise construct models for unobserved outcomes if more than 20% of participants are missing follow-up data for any reason.

6.7 Safety and Tolerability Analysis

6.7.1 Treatment-emergent Adverse Events

The incidence of TEAEs will be summarized by the number of events of a given classification experienced by participants in each treatment group and by the number and proportion of participants experiencing such an event in each treatment group in the ST sample. TEAEs will be summarized in aggregate across all MedDRA terms and separately by MedDRA system organ class and preferred term.

Aggregate summaries of TEAE grade will include characteristics of: (a) seriousness, (b) severity, (c) relatedness to study drug, (d) action taken with study drug, (e) action taken with study procedure, and (f) outcome. For each level of a given TEAE characteristic, summaries will include the number of events of a given classification and by the number and proportion of participants for which that level of a characteristic was the worst they experienced (treating any unknown characteristic as not worst).

6.7.2 Safety Labs

The absolute level and the absolute change from baseline for each safety laboratory assay will be summarized as means, standard deviations, medians, and ranges at each visit by treatment group. The proportion of participants with safety lab levels below the lower limit of normal or above the upper limit of normal will be summarized by treatment group by visit and at any post-baseline visit.

6.7.3 Vital Signs

The absolute level and the absolute change from baseline for vital signs will be summarized as means, standard deviations, medians, and ranges at each visit by treatment group.

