## 3) Correlations between Serum Urate and Hypertension

A positive association between baseline serum urate and risk of developing hypertension has been consistently observed in numerous longitudinal studies, and seems to be independent from other known risk factors.  In recent studies in which relative risk estimates were adjusted for baseline body mass index, blood pressure, and other potential confounding factors, the increased risk of

hypertension seems to be linear, without obvious threshold effects. The relative risk associated with a 1.0 mg/dL difference in serum urate concentrations ranged from 1.09 (95% CI: 1.02 to 1.17) among 3,073 men followed for six years as part of the Multiple Risk Factors Intervention Trial (MRFIT) to 1.31 among 2,520 individuals (men and women) followed for 10 years as part of the Beaver Dam Study; the pooled relative risk was 1.13 (95% CI: 1.06 to 1.20) in a 2011 meta-analysis. Results of the same meta-analysis suggested that the association between urate and hypertension tends to be stronger at younger ages and in women. An increase in blood pressure has also been found among individuals who did not develop hypertension during the follow-up. For example, a 1.0 mg/dL increase in serum urate concentration was found to be associated with a 2.5 mm Hg increase in systolic blood pressure (SBP) and a 1.2 mm Hg increase in diastolic blood pressure (DBP) after 5-years of follow-up in the Beaver Dam Study, whereas a smaller average increase was reported over a one year period in the MRFIT (0.33/0.16 mm Hg, SBP/DBP).

However, recent studies in humans with MS and PD (see below) on the effects of urate-elevating inosine found no detectable effect on blood pressure (SBP, DBP or their orthostatic changes) of inosine that elevated serum urate by up to 4 mg/dL to achieve chronic stable levels of 7-8 mg/dL. Thus any increase in blood pressure attributable to urate elevation that might be observed in SURE-PD3 would likely be modest. Further, among individuals with PD, blood pressure tends to decline early in the disease course. Nevertheless, blood pressure will be closely monitored during the trial and anti-hypertensive treatment will be initiated or adjusted as needed.

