4.3 Efficacy Endpoints

The primary outcome of the trial is rate of change in MDS-UPDRS I-III total score over 24 months estimated in the ITT sample from a shared-baseline, random-slopes mixed model, censoring follow-up of subjects after initiation of dopaminergic therapy.

Secondary efficacy endpoints include the following:

- MDS-UPDRS scores: Parts I, II, III, IV, ambulation, and patient-reported sections (Parts IB and II),
- Striatal DAT binding by DaTscanTM,
- Neuro-QOL module scores: Lower Extremity Function, Upper Extremity Function, Anxiety, Depression, Positive Affect and Well-being, Cognitive Function, Fatigue, Sleep Disturbance, Emotional and Behavioral Dyscontrol, Communication, Ability to Participate in Social Roles and Activities, Stigma, and Satisfaction with Social Roles and Activities,
- Montreal Cognitive Assessment (MoCA) score to assess cognition,
- Parkinson's Disease Questionnaire 39 item version (PDQ-39) score to assess quality of life,
- Modified Schwab and England ADL score to assess functional disability,
- Orthostatic vital signs: supine to standing change in systolic blood pressure, diastolic blood pressure, and heart rate; orthostatic hypotension, and
- Medical intervention: levodopa equivalent daily dosage, disability warranting initiation of dopaminergic therapy.

Exploratory efficacy endpoints include: REM sleep behavior disorder (RBD) symptoms and symptom severity, quantitative measures derived from tasks completed using the Smart4SURE implementation of the mPower smartphone app.

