4.5 Safety Endpoints

The following safety endpoints will be evaluated:

- Overall TEAE and serious TEAE incidence rate,
- Time to first serious TEAE,
- Proportion of participants experiencing and number of unique events of each type of TEAE and serious TEAE classified by MedDRA system organ class and preferred term,
- Proportion of participants experiencing and number of unique events of each type of TEAE within the group of events specified as of special interest,
- Proportion of participants experiencing and number of unique events of TEAEs classified by seriousness, severity, relatedness to study drug, action taken with study drug, and outcome, summarized across all MedDRA terms,
- Mean change from baseline in safety labs: complete blood count, leukocyte differential, electrolytes, renal panel, liver function tests, lipid profile, thyroid stimulating hormone, and urinalysis of spot and 24-hr samples,

- Mean change from baseline in blood pressure (supine and standing), heart rate (supine and standing), orthostasis (change from supine to standing), and body weight,
- Mean change from baseline in ECG parameters,

Reported proportions will use as their denominator all participants in the Safety and Tolerability sample (see Section 5.2 below).

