6.7.4 Additional Continuous Safety Outcomes

The additional continuous safety outcomes of weight, ECG parameters, and their absolute change from baseline will be summarized as means, standard deviations, medians, and ranges at each visit by treatment group and tested for group differences in linear mixed models.

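### Mean supine and standing blood pressure is a named safety endpoint, but the SAP only tabulates it by visit, so no between-arm difference with a confidence interval is planned

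*SAP*

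**What the plan says.** SAP 4.5 (Safety Endpoints) lists "Mean change from baseline in blood pressure (supine and standing), heart rate (supine and standing), orthostasis (change from supine to standing), and body weight". Blood pressure and body weight therefore stand in the same item.

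The analysis sections then treat them differently:

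- SAP 6.7.3 states: "The absolute level and the absolute change from baseline for vital signs will be summarized as means". The tables are by visit and arm and also carry SDs, medians and ranges. No model, test, difference or interval is mentioned.
- SAP 6.7.4 (Additional Continuous Safety Outcomes): weight, ECG parameters and their changes are "summarized as means, standard deviations, medians, and ranges at each visit by treatment group and tested for group differences in linear mixed models".

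Three other parts of the plan bear on pressure:

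- SAP 4.3 lists as secondary efficacy endpoints "Orthostatic vital signs: supine to standing change in systolic blood pressure, diastolic blood pressure, and heart rate; orthostatic hypotension", and SAP 6.6.3 models them.
- SAP 3.3 compares the arms on the proportion with clinically significant abnormal vital signs. Protocol 10.5.7 assigns Fisher's exact test to that proportion; SAP 6.7 does not restate a test.
- SAP 6.7.1 summarises treatment-emergent adverse events by arm and preferred term, so reported hypertension would be counted.

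The protocol's section on serum urate and hypertension (2.2.2 A 3) says "blood pressure will be closely monitored during the trial" and that antihypertensive treatment will be started or adjusted as needed. Protocol 6.1.2 schedules pressure at Screening Visit 2, Baseline, Week 12, Month 12, Month 24 and Month 27. That is two readings before dosing, three in the treatment period and one after wash-out.

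**The concern.** The protocol names hypertension among the possible harms to be weighed against benefit, and it describes the association between urate and hypertension as consistent across longitudinal studies. A trial that deliberately raises urate for two years and measures pressure six times can put a randomised estimate on that question. As written, the SAP stops at tables of visit means.

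Visit tables have two weaknesses here. They do not combine the two pre-dose and three on-treatment readings into one estimate. Each visit also reports whoever attended, and SAP 4.6 and 4.8 record an early closeout notified to sites on 25 October 2018, so the later visits may hold fewer people and a different mix.

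The other planned analyses answer different questions. The postural model looks at the difference between supine and standing pressure; if both rise by the same amount, that difference does not move. A proportion above a clinical threshold and a count of adverse events register individual excursions, not a shift of a few mm Hg in the mean.

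**Working it through.** **1. Arm size.** The plan gives no precision or power figure for blood pressure, so its own sample size is used to fix the arm size. Inputs from SAP 3.8: a difference of 6.3 points over 24 months = 0.2625 per month, SD 0.758 per month, two-sided alpha 0.046, power 80%.

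n per arm = 2 × (1.995 + 0.842)² × 0.758² / 0.2625² = 134.2, rounded up to 135, or 270 in total. The plan's figure reproduces.

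**2. Size of effect in the documents' own figures.** Protocol 2.2.2 A 3 cites, per 1 mg/dL of urate, 0.33/0.16 mm Hg (systolic/diastolic) over one year in one cohort and 2.5/1.2 mm Hg after five years in another. SAP 3.7 expects an average rise of 3 mg/dL.

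- Lower: 3 × 0.33 = 1.0 systolic; 3 × 0.16 = 0.5 diastolic.
- Upper: 3 × 2.5 = 7.5 systolic; 3 × 1.2 = 3.6 diastolic.

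These are products of observational slopes. The same protocol section reports that inosine studies in multiple sclerosis and PD, raising urate by up to 4 mg/dL, found no detectable effect on blood pressure, and it expects any rise to be modest.

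**3. Precision available.** Neither document gives a systolic SD or within-person correlation. Assumed: SD 14-18 mm Hg, equal correlation r = 0.5-0.7 between any two readings, 135 per arm, every reading present. Let k = √(2/135) = 0.1217.

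*Change from one baseline to one visit:* SE = SD × √(2(1 − r)) × k.

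- SD 14, r 0.7: 14 × 0.775 × 0.1217 = 1.3
- SD 18, r 0.5: 18 × 1.000 × 0.1217 = 2.2

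*Mean of three on-treatment readings, adjusted for the mean of two baseline readings:* SE = SD × √[(1 + 2r)/3 − 2r²/(1 + r)] × k.

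- r 0.7: 0.800 − 0.576 = 0.224, square root 0.473; 14 × 0.473 × 0.1217 = 0.81
- r 0.5: 0.667 − 0.333 = 0.333, square root 0.577; 18 × 0.577 × 0.1217 = 1.26

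The difference detectable with 80% power at two-sided 0.05 is 2.8 × SE:

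| Analysis | SE (mm Hg) | Detectable (mm Hg) |
|---|---|---|
| Single-visit change | 1.3-2.2 | 3.7-6.1 |
| Adjusted three-visit mean | 0.8-1.3 | 2.3-3.5 |

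**4. Where the gain comes from, and how it erodes.** A single visit adjusted for one baseline has SE = SD × √(1 − r²) × k: 14 × 0.714 × 0.1217 = 1.2, and 18 × 0.866 × 0.1217 = 1.9. So part of the gain is baseline adjustment, and the rest comes from averaging visits and using both baseline readings.

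If only Week 12 contributed, with both baselines, SE = SD × √[1 − 2r²/(1 + r)] × k: 14 × 0.651 × 0.1217 = 1.1, and 18 × 0.816 × 0.1217 = 1.8. Early closeout would put the real figure somewhere between this and the complete-data figure.

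**The case against.** A reader might infer that blood pressure gets no between-arm comparison, or that only falls are compared. The documents do not support either. SAP 3.3 compares arms on clinically significant abnormal vital signs, and orthostatic hypotension is given as one inclusion, so a clinically significant rise is not excluded. Protocol 10.5.7 tests that proportion. The SAP supplements the protocol and overrides it on analysis only where they disagree, so its silence on the test arguably leaves the Fisher comparison in force. Hypertension adverse events are also tabulated by arm. All of this stands. It shows routes by which a rise could be noticed, but none of them yields a mean difference.

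A reader might also take 7.5 mm Hg as the rise the documents predict. It is not. It is an observational slope after five years, multiplied up, for a trial that treats for two years. Protocol 2.2.2 A 3 sets null inosine data beside it. SAP 2.6 also records a cut in maximum dosage from 3.0 to 2.0 gm/day from 24 January 2018, which may reduce the 3 mg/dL rise used in the multiplication. Against that, the earlier PD study had 75 participants in three arms, and protocol 3.2.4.3 itself says its size and follow-up were too small to give substantial reassurance on cardiovascular events.

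Nor does SAP 6.7.4 promise weight and ECG an adjusted estimate: it names no covariates and commits only to a test.

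Finally, a reader could form a crude difference and interval from the tabulated Ns, means and SDs, and safety labs (SAP 6.7.2) get the same descriptive treatment. Both are true. The crude interval would be wider, would use one visit at a time, and is not something the plan commits to report.

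**Conclusion.** The point holds as a minor, easily repaired gap. SAP 4.5 names mean blood pressure as a safety endpoint, and nothing in either document plans a between-arm difference with a confidence interval for it, while weight, listed beside it, is given a mixed-model test without any stated reason for the distinction.

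On the assumed SD, correlation and complete data, the existing readings would support an SE of about 0.8-1.3 mm Hg. That is enough to detect or exclude much of the 1 to 7.5 mm Hg span, but not its lower end. The SE is a best case because of early closeout. Blood pressure is one of several cardiovascular concerns in the protocol, alongside coronary disease and stroke, and nothing here suggests that a pressor effect is likely.

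**What to change.** In SAP 6.7.4, add supine and standing systolic and diastolic pressure and heart rate to the linear mixed models, in the ST sample. Use a shared baseline built from the Screening Visit 2 and Baseline readings, with visit by treatment terms at Week 12, Month 12 and Month 24. Report the average on-treatment difference with its 95% CI, and keep the 6.7.3 tables.

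Add one sensitivity analysis that accounts for antihypertensive medication started or changed after baseline. The protocol itself provides for such changes, and they could hide a rise. An analysis leaving out readings after dopaminergic initiation is not advised: it would select on a post-randomisation event, and SAP 3.6 already describes those who have not started therapy by the end of period 1 as a non-random, slow-progressing subset.

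The cost is a few sentences in the SAP and a few more model runs. The downside is more safety comparisons; reporting them as intervals without p-values limits that. No extra data collection is needed.

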6.7.4 Additional Continuous Safety Outcomes

The additional continuous safety outcomes of weight, ECG parameters, and their absolute change from baseline will be summarized as means, standard deviations, medians, and ranges at each visit by treatment group and tested for group differences in linear mixed models.

6.7.5 Tolerability

Participants will be classified as tolerant, intolerant, or censored with subjects lost to follow-up or withdrawing consent prior to administrative termination classified as intolerant. Tolerability will then be estimated from Kaplan-Meier product-limit methods with complementary log-log confidence bounds at 12 weeks, 12 months, and 24 months. Serum urate elevation will be declared tolerable at each time point if its one-sided lower 95% confidence bound is greater than 50%. We will explore the relationship between tolerance and use of dopaminergic therapy using Cox regression with use of dopaminergic therapy as a time-dependent covariate.

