Cardiovascular	5 (16)	0	1 (4)	6 (7)
Acute coronary syndrome	1 (4)	0	0	1 (1)
Atrial fibrillation	1 (4)	0	0	1 (1)
Cerebrovascular accident	1 (4)	0	0	1 (1)
Coronary artery disease	0	0	1 (4)	1 (1)
Palpitations	1 (4)	0	0	1 (1)
Tachycardia	1 (4)	0	0	1 (1)
Goutlike symptoms	1 (4)	3 (8)	2 (7)	6 (7)
Arthralgia of toe(s) c	1 (4)	2 (4)	1 (4)	4 (5)
Swelling of toe(s) d	0	1 (4)	1 (4)	2 (3)
Urolithiasis or its symptoms	0	2 (2)	2 (2)	4 (5)
Hematuria	0	1 (4)	0	1 (1)
Nephrolithiasis	0	1 (4)	2 (7)	3 (4)
Overall	6 (20)	5 (17)	5 (19)	16 (19)

<sup>a Medical Dictionary for Regulatory Activities system organ class and preferred terms.
bValues show total number of events (% of participants).

Arthralgia of toes combines the following preferred terms in instances where the verbatim complaints mentioned feet or toes: arthralgia and pain in extremity.
 Swelling of toes combines the following preferred terms in instances where the verbatim complaints mentioned feet or toes: joint swelling and local swelling.

Abbreviations: Ino→Mild, inosine dosed to mildly elevate urate; Ino→Mod, inosine dosed to moderately elevate urate. [Adapted from Ref. 102.]

did not differ between treatment groups. For example, serial vital signs, serum assays, and electrocardiograms (ECGs) showed no effect of inosine on blood pressure (or its orthostatic changes), body mass index, serum glucose and cholesterol levels, or ECG parameters. And despite the increased frequency of urolithiasis while receiving inosine, there were no other renal SAEs and renal function as assessed by serum creatinine and estimated glomerular filtration rate remained unchanged from baseline in all groups.

Treatment was tolerated by 95% of subjects at 6 months (Fig. 5A), and no subject withdrew due to an adverse event. Similarly, retention and compliance were excellent, with 99% completing the study and 100% of placebo subjects maintaining a mean serum urate within the baseline range (<6.0 mg/dL), consistent with no surreptitious use of OTC inosine. Thus a high proportion tolerated and maintained the assigned treatment, and overall safety results were reassuring. Nevertheless, urolithiasis remains a

[figure not shown]

Figure 5. Tolerability of Inosine and Its Effects on Serum and CSF Urate Levels.

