## 10.5.7 Safety and Tolerability Outcomes

Overall AE and SAE rates will be compared between treatment groups by negative binomial regression. Time to first SAE will be compared between treatment groups by Kaplan-Meier logrank test. The proportion of subjects experiencing (a) each type of AE, classified by MedDRA preferred term and system organ class, (b) clinically-significant abnormal labs, and (c) clinically significant abnormal vital signs, including orthostatic hypotension defined as positional dizziness or other clinical symptoms of orthostatic hypotension or a drop in systolic and diastolic blood pressures of 20 mm Hg and 10 mg Hg or more, respectively, when moving from a supine to a standing position will be compared between treatment groups by Fisher's exact test.

Assuming no administrative censoring, all subjects will be classifiable as tolerant or intolerant, with subjects lost to follow-up or withdrawing consent classified as intolerant. Tolerability will then be estimated by simple proportions tolerant at 12 weeks and 24 months. Serum urate elevation will be declared tolerable at each time point if its exact one-sided lower 95% confidence bound is greater than 50%. If evaluation of tolerance is censored, then Kaplan-Meier product-limit estimates and their complementary log-log confidence bounds will be used. We will explore the relationship between tolerance and use of dopaminergic therapy using Cox regression with use of dopaminergic therapy as a time-dependent covariate.

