3.4 Tolerability

Tolerance of treatment by an individual participant will be defined as remaining on-study and on his/her assigned treatment without one or more AE-associated dosage reductions lasting more than 4 weeks cumulative. Tolerability of oral inosine titrated to achieve trough serum urate in the range 7.1 to 8.0 mg/dL will be defined as the proportion of all participants in the active arm who are tolerant of the treatment at 12 weeks (short-term), 12 months (medium-term), and 24 months (long-term). Oral inosine titrated to achieve trough serum urate in the range 7.1 to 8.0 mg/dL will be declared tolerable for a given duration of treatment if the proportion who are tolerant is significantly greater than 50%.

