4.6 Tolerability Endpoint

Tolerance of treatment by an individual participant will be defined as remaining on-study and on his/her assigned treatment without one or more AE-associated dosage reductions lasting more than 4 weeks cumulative. Tolerance will only be assessed through 24 Oct 2018, the day before clinical sites were notified of early study closeout, as discontinuation of study drug after that date may reflect a change in participants' or investigators' equipoise. Tolerability of oral inosine titrated to achieve trough serum urate in the range 7.1 to 8.0 mg/dL will be defined as the proportion of all participants in the active arm who are tolerant of the treatment at 12 weeks (short-term), 12 months (medium-term), and 24 months (long-term). Oral inosine titrated to achieve trough serum urate in the range 7.1 to 8.0 mg/dL will be declared tolerable for a given duration of treatment if the proportion who are tolerant is significantly greater than 50%.

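### The tolerability declaration tests the inosine arm against a fixed 50% floor, and no between-arm comparison of tolerance is planned, so intolerance caused by inosine cannot be told from background attrition

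*SAP*

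**What the plan says.** SAP 4.6 defines tolerance for a participant as "remaining on-study and on his/her assigned treatment without one or more AE-associated dosage reductions lasting more than 4 weeks cumulative". It then defines tolerability of the regimen as "the proportion of all participants in the active arm who are tolerant of the treatment" at 12 weeks, 12 months and 24 months. SAP 3.4 says that inosine "will be declared tolerable for a given duration of treatment if the proportion who are tolerant is significantly greater than 50" per cent.

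SAP 6.7.5 gives the method: "Kaplan-Meier product-limit methods with complementary log-log confidence bounds at 12 weeks, 12 months, and 24 months". Its decision rule reads: "Serum urate elevation will be declared tolerable at each time point if its one-sided lower 95% confidence bound is greater than 50" per cent. Participants lost to follow-up or withdrawing consent before administrative termination are classed as intolerant. The only further model there relates tolerance to use of dopaminergic therapy, not to treatment. SAP 4.6 stops the assessment of tolerance at 24 October 2018, the day before sites were told of early closeout.

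Protocol 10.5.7 has the same bar with a different bound: "Serum urate elevation will be declared tolerable at each time point if its exact one-sided lower 95% confidence bound is greater than 50" per cent. Protocol 10.2.2.2 words the definition for a treatment group in general; the SAP narrows it to the active arm. Neither document gives a reason for 50%. SAP 3.9 states the operating characteristic: an 80% probability of the declaration at a true tolerant proportion of at least 62%.

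**The concern.** Safety and tolerability form a stated secondary objective of a randomised trial with matched capsules and matched titration. The tolerance composite mixes drug effects with attrition that would occur on any capsule, and sample size planning allows up to 8% loss to follow-up before dopaminergic therapy. A single-arm proportion cannot separate the two; the placebo arm can.

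The separation matters here. SAP 2.6 records that the maximum dosage was lowered in January 2018 because of a higher than expected rate of kidney stones. Readers of the results will want to know how much intolerance inosine adds. A declaration against an absolute floor does not answer that, and the plan contains no estimate that does.

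**Working it through.** **Inputs.** 270 randomised 1:1, so 135 per arm (SAP 3.8). One-sided 95% lower bound against 50% (SAP 6.7.5). Stated power 80% at 62% (SAP 3.9). Phase 2 experience (Protocol 2.2.3): "Treatment was tolerated by 95% of subjects at 6 months", given in the text without a split by arm. Neither document states tolerance rates by arm for this trial, so the placebo and inosine rates in steps 4 and 5 are assumptions.

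**1. The plan's own figure.** One-sample normal approximation with null variance:

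power = Φ{[(0.62 − 0.50)·√135 − z·0.5] / √(0.62 × 0.38)}

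- z = 1.960 (one-sided 0.025): 80.3%, which reproduces the stated 80%.
- z = 1.645 (one-sided 0.05, as the rule is written): 88.1%; the exact binomial version gives 86.4%.

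The stated 62% is therefore slightly conservative for the written rule, which reaches 80% power at a true 60.9%.

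**2. Passing count.** The exact one-sided 95% lower bound is 0.496 for 77/135 and 0.503 for 78/135. So 78/135 = 57.8% passes.

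**3. Probability of passing, P(X ≥ 78), X ~ Binomial(135, p).**

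| True inosine tolerance p | P(declared tolerable) |
|---|---|
| 50% | 0.042 |
| 55% | 0.288 |
| 60% | 0.732 |
| 62% | 0.864 |
| 65% | 0.966 |
| 70% | 0.999 |
| 75% | 1.000 |

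**Allowing for the SAP's estimator.** A simulation of the Kaplan-Meier complementary log-log bound at 24 months (135 participants, exponential time to intolerance, 4,000 replicates) gave, without censoring, 0.861 at 62% and 0.999 at 70%. Two assumed closeout patterns gave:

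| True 24-month tolerance | Censoring uniform on 8–30 months | Censoring uniform on 4–28 months |
|---|---|---|
| 62% | 0.69 | 0.58 |
| 70% | 0.97 | 0.92 |
| 75% | 0.998 | 0.98 |

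**4. What a between-arm comparison could show.** Two proportions, 135 per arm, two-sided 0.05, no censoring:

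power = Φ{(d − 1.96·s₀)/s₁}, with s₀ = √[2p̄(1−p̄)/135] and s₁ = √{[p₁(1−p₁) + p₂(1−p₂)]/135}.

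For 85% against 70%: d = 0.15, s₀ = 0.0508, s₁ = 0.0500, so Φ(1.01) = 84%. For 90% against 70%: d = 0.20, s₀ = 0.0487, s₁ = 0.0471, so Φ(2.22) = 99%.

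| Placebo / inosine (assumed) | 50% rule passes | Between-arm power |
|---|---|---|
| 85% / 70% | 99.9% | 84% |
| 90% / 75% | about 100% | 90% |
| 90% / 70% | 99.9% | 99% |
| 85% / 65% | 97% | 97% |

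**5. Precision.** For 85% against 70%, the 95% interval for the difference would have a half-width of about 1.96 × 0.0500 = 0.098, or 10 points, before censoring.

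**The case against.** The strongest reply is that the 50% bar is a disclosed design choice with a stated operating characteristic. An absolute floor asks whether most people can stay on the regimen, which is a legitimate question, and attribution is left to the adverse event comparisons. That stands as a defence of keeping the floor: replacing it would be a design preference. It does not explain why the composite is left uncompared.

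Two stronger readings are tempting, and the documents support neither.

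- A reader might infer that the rule passes whatever inosine does. It does not: intolerance caused by inosine lowers the tested proportion directly, and the rule passes only 4% of the time at a true 50% and 29% at 55%. Nor is near-certain passing at high tolerance a fault in itself; a drug that adds no intolerance should pass.
- A reader might infer that the placebo arm is never used. SAP 4.8 and 6.8.1 summarise discontinuation and withdrawal by arm, SAP 6.7.1 summarises events by action taken with study drug in each arm, and SAP 3.3 compares adverse event rates between arms. These overlap with the composite, but none counts adverse-event-associated dose reductions exceeding 4 weeks cumulative, and none gives a tolerance estimate for placebo or a difference with an interval.

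It is also fair to say that phase 2 is a weak guide. The 95% is at 6 months and not split by arm, and Protocol 3.2.2 expects higher urate and more adverse event risk under trough sampling.

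**Conclusion.** The point holds as a gap in the tolerability analysis: the declaration rests on one arm against an absolute floor, and no between-arm contrast of tolerance is planned. The near-certain declaration applies where true inosine tolerance is about 65 to 70% or more without censoring; at 24 months under closeout censoring it is less certain, about 92 to 97% at 70%. That censoring would also lower the between-arm power below the uncensored 84 to 99%. The size of any masked deficit depends on assumed placebo tolerance of 85 to 90% and on the assumed censoring patterns. The gap itself, the absence of any planned estimate of excess intolerance, depends on neither. It is an inexpensive improvement that should be made, and it does not affect the primary analysis.

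**What to change.** In SAP 6.7.5, and to match in 3.4 and 4.6:

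- Estimate Kaplan-Meier tolerability in both arms of the Safety and Tolerability sample, with the same definition and the same 24 October 2018 cut-off.
- Report the inosine-minus-placebo difference with 95% confidence intervals at 12 weeks, 12 months and 24 months.
- Add a logrank or Cox comparison of time to intolerance.
- Keep the 50% rule as the stated absolute floor, and report any declaration of tolerability together with the between-arm difference.

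The cost is a few lines of SAP text and one more nominal analysis. The data are already collected in both arms and no alpha is needed, since SAP 6.6.10 already reports secondary efficacy and subgroup results with nominal p-values. The downside is that the tolerability statement becomes less automatic.
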